6.5.7. CGI-S Scale (global, physician rated)

6.5.7.1. Definition

For a detailed description of the scale, refer to the Section 6.3.8 of the study protocol.

The CGI-S is administered at screening, baseline, week 3, week 7, week 9, week 12, week 15/ET, and week 16/EOS visits.

6.5.7.2. Analysis

The CGI-S change from baseline to week 15 data will be analyzed using MMRM similarly to the description in Section 6.5.1.2. CGI-S baseline assessment will be used as the corresponding baseline value.

6.5.8. Response Analysis

The following response analyses will be performed:

- CaGI-I response, defined as patients who are described by the caregiver as “Much Improved” or “Very Much Improved” in the CaGI-I score;
- CGI-I response, defined as patients who are described as “Much Improved” or “Very Much Improved” in the CGI-I score;
- CGI-S response, defined as patients who have a reduction of ≥ 1 point in the CGI-S score;
- PGI-I response, defined as patients who are described as “Much Improved” or “Somewhat Improved” in the PGI-I score.

The proportion of patients answering each response definition above will be calculated as the number of patients answering each response definition above in each treatment group divided by the number of patients in the given treatment group at each visit where the corresponding scale was assessed. The proportion of responder patients will be compared between groups using the Cochran–Mantel–Haenszel test adjusting for age group at baseline and region.

The responder patient counts and percentages will be presented at each visit.

As a sensitivity analysis, proportion of responder patients for each criterion will also be summarized and analyzed as described above by classifying patients with missing data at a visit as a non-responder, meaning the entire mITT analysis set population participates in the analysis.

6.6. Minimal Clinically Important Difference (MCID) and Minimal Clinically Important Change (MCIC) Exploratory Analysis

[REDACTED]

6.6.1. Descriptive Statistics of MD-CRS part II vs Global Impression of Improvement at Week 15

For each anchor, the change from baseline in MD-CRS part II vs CaGI-I, CGI-I, and PGI-I at week 15 will be presented graphically.

In addition, the mean change from baseline in MD-CRS part II vs global impression of improvement at week 15 will be summarized by treatment group as follows:

For CaGI-I, CGI-I as anchors:

	Mean Change from Baseline in MD-CRS part II					
	TEV-50717		Placebo		All	
	N	Mean (SE)	N	Mean (SE)	N	Mean (SE)
Very Much Improved						
Much Improved						
Minimally Improved						
Not Changed						
Minimally Worse						
Much Worse						

For PGI-I as anchor:

	Mean Change from Baseline in MD-CRS part II					
	TEV-50717		Placebo		All	
	N	Mean (SE)	N	Mean (SE)	N	Mean (SE)
Much Improved						
Somewhat Improved						
Not Changed						
Somewhat Worse						
Much Worse						

6.6.2. MCID Analysis

The MCID analysis will be based on the method described by Hauser et al (2014). According to this method, the MCID is defined as the difference between patients in the TEV-50717 group who were rated “Minimally Improved” and patients in the placebo group who were rated “No Change”. The calculation will be performed for each anchor (CaGI-I, CGI-I and PGI-I) separately².

The MCID analyses will be performed if there are at least 5 patients in the TEV-50717 group and at least 5 patients in the placebo group who contribute to the calculation.

² For PGI-I, the level “Somewhat Improved” will be used instead of “Minimally Improved”.

6.6.3. MCIC Analysis

The MCIC analysis will be based on the method described by Hauser et al (2022). According to this method, the MCIC is defined as the mean change from baseline in MD-CRS part II in patients treated with TEV-50717 who were rated “Minimally Improved”.

If the mean change from baseline in MD-CRS part II at week 15 for the patients in the placebo group who were rated “No Change” is negative, indicating a placebo effect in this subgroup, then the MCIC analysis will not be carried out.

The MCIC analyses will be performed if there are at least 5 patients in the TEV-50717 group who contribute to the calculation.

6.6.4. Descriptive Statistics of Improvement in MD-CRS part II

The following descriptive statistics for the change from baseline in MD-CRS part II by treatment group will be added: a histogram of the change; cumulative distribution of improvement (i.e., proportion of patients with change ≤ 0 ; change ≤ -1 ; change ≤ -2 ; change ≤ -3 , change ≤ -4 , ...).

7. MULTIPLE COMPARISONS AND MULTIPLICITY

The primary efficacy endpoint will be tested at the 1-sided significance level of $\alpha=0.025$.

If the primary endpoint is statistically significant (p-value ≤ 0.025), the 5 key secondary hypotheses will be tested using a hierarchical approach at the 1-sided significance level of $\alpha=0.025$, in the following order: (1) MD-CRS part I total score, (2) CaGI-I, (3) CGI-I, (4) UHDRS-TMC (centrally-read), and (5) UHDRS-TMD (centrally-read)

No multiplicity control will be applied to the sensitivity analysis or other endpoints.

8. SAFETY ANALYSIS

8.1. General

Safety analyses will be performed on the safety analysis set (Section 3.3), unless otherwise noted. Summaries will be presented by treatment group and for all patients, unless otherwise stated. Selected safety data might also be presented by age group, as applicable.

For continuous variables, descriptive statistics will be provided for actual values and changes from baseline to each time point. For categorical variables, patient counts and percentages will be provided.

Safety assessments and time points are provided in Table 3 of the study protocol.

8.2. Duration of Exposure to Study Drug

Duration of exposure to study drug (days) for individual patients is the number of days patient received drug (last day of study drug – first day of study drug + 1). Duration of treatment (days) will be summarized using descriptive statistics. Weeks on treatment using the categories ≤ 3 weeks, >3 to ≤ 7 weeks, >7 to ≤ 9 weeks, >9 to ≤ 12 weeks, >12 to ≤ 15 and >15 weeks will also be summarized using descriptive statistics.

8.3. Adverse Events

Adverse events will be collected and recorded from the time a patient signs the informed consent to the end of follow-up period. For this study, the follow-up period for recording of adverse events is defined as 2 weeks after the last dose of IMP or up to baseline/day 1 in the open-label safety extension study TV50717-CNS-30081 (whichever comes first) or 2 weeks after last site visit for patients who terminated early from the study.

All adverse events will be coded using MedDRA. Each patient will be counted only once in each preferred term or SOC category for the analyses of safety. Unless otherwise specified, adverse events will be summarized by SOC and preferred term, with SOCs and preferred terms within SOCs presented in descending order of patient incidence. Summaries will be presented for all adverse events (overall and by severity), adverse events determined by the investigator to be related to test IMP (ie, reasonable possibility; see Table 7 of the study protocol - defined as related or with missing relationship), overall and by severity, serious adverse events, and adverse events causing withdrawal from the study; Most common adverse events, defined as occurring in $> 4\%$ of the patients in either of the treatment groups overall, and by preferred term. Summaries will be presented by treatment group and for all patients.

Summaries will include treatment-emergent adverse events which are defined as adverse events occurring at or after the first dose of the IMP. The listings will include all adverse events recorded.

Patient listings of all adverse events, serious adverse events, adverse events leading to study drug discontinuation, adverse events leading to dose interruption and adverse events leading to death will be presented. Patient's dose at the time of the AE onset will be included in all listings.

8.4. Deaths

If any patient dies during the study, a listing of deaths will be provided, and all relevant information will be discussed in the patient narrative included in the CSR.

8.5. Clinical Laboratory Tests

Summary statistics for chemistry, hematology and coagulation, and urinalysis laboratory tests are assessed at screening and week 15. The assessment will be repeated at week 16 visit for patients with clinically significant laboratory abnormalities at week 15. Laboratory values and changes from baseline to week 15 and the last assessment as defined in Section 4.4 will be presented.

A list of laboratory tests is included in Table 8 of the study protocol.

Shifts (below, within, and above the normal range) from baseline to last assessment will be summarized using patient counts for all the laboratory tests as applicable. Only patients with both baseline and post-baseline assessments will be summarized in the shift tables.

Only central laboratory assessments will be summarized; local laboratory assessments will be listed. Values below the lower limit of quantification or above the upper limit of quantification will be assessed on a case-by-case basis if present in the data and discussed in the final blinded SDR meeting.

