Maintenance period (8 weeks): Patients will continue to receive their maintenance dose over the next 8 weeks, although a 1-time dose reduction (to the previous dose level for the remainder of the study) for adverse events is allowed. Patients will return to the clinic at weeks 9, 12, and 15 for assessments of efficacy and safety.

Washout period and follow-up: All patients will discontinue IMP at the week 15 visit and will return 1 week later for the end-of-study (EOS) visit. Patients who complete the study may be eligible to begin participation in the open label safety extension Study TV50717-CNS-30081 at that time. At the week 16 visit, patients may choose to enter Study TV50717-CNS-30081 (on

¹ The titration scheme is presented in Tables 4 and 5 in the study protocol.

that day) or up to 1 week later (2 weeks from the week 15 visit). Patients who complete treatment but choose not to participate in the open-label safety extension Study TV50717-CNS-30081 before week 17 of Study TV50717-CNS-30080 will be contacted for a safety evaluation call occurring 2 weeks after their last dose of IMP.

The study scheme is presented in [Figure 1](#).

At the time of informed consent, the parent/legal guardian will be counseled that, once randomized to treatment, patients are to remain in the study and complete all study procedures unless the choice is made to withdraw consent. Patients who withdraw from the study before completing the 15 week treatment period should have an early termination (ET) visit as soon as possible after the last dose of IMP. All patients who discontinue early will have a follow-up telephone contact for safety evaluation 2 weeks after ET; evaluations will be as described for week 17.

[figure not shown]
Patients who screen fail or terminate early from the study due to emergency circumstances (such as coronavirus disease 2019 [COVID-19]) may be allowed to re-screen/re-enter (respectively) the study at a later date, depending on the circumstances.

Study procedures and assessments with their timing are summarized in Table 3 of the study protocol.

Interim Analysis: When approximately 50 patients have completed the study (including follow-up), an independent Data Monitoring Committee (iDMC) will perform an unblinded non-binding IA for futility based on centrally read MD-CRS part II total score.

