	≥Day after EOT	Day 112	Week 16
Laboratory tests other than pregnancy and drug screen	Day 2 – EOT	Day 105	Week 15
	≥Day after EOT	Day 112	Week 16
Orthostatic blood pressure, Physical exam, Neurological exam, height, CBCL-full assessment	Day 2 – EOT	Day 105	Week 15

^a CBCL=Child Behavior Checklist (for ages 6-18); C-SSRS=Columbia-Suicide Severity Rating Scale; ECG=electrocardiogram; ESRS=Extrapyramidal Symptom Rating Scale (subscales I and II); ESS =Epworth Sleepiness Scale (for children and adolescents); EOT=end of treatment

After mapping the data to the analysis visits of unscheduled and early termination visits, the following rules will apply unless other handling is specified for a particular analysis:

- If there is a scheduled visit in the analysis window, the last non- missing scheduled visit will be selected.
- If there is no scheduled visit, but early termination visit, early termination visit will be selected.

- If there are no scheduled or early termination visits, the record closest to the planned assessment day will be selected for analysis.
- If there are no scheduled or early termination visits, and 2 records are equidistant from the scheduled day, then the later record will be selected.
- If a patient has no scheduled record or early termination/unscheduled visits in an analysis window, the patient will be considered missing at that visit.

For these analyses performed by time period, eg, adverse events, the following definitions will be used:

- Titration Period - from the first dose of treatment until the day of the week 7 visit. For patients discontinued before the week 7, the Titration Period is until the later of the last dose of treatment and the early termination visit.
- Maintenance Period - from the day after the week 7 visit until the day of the week 15 visit. If a patient enters the Maintenance Period but discontinues treatment early, the Maintenance Period is until the later of the last dose of treatment and the early termination visit.
- Overall Treatment Period - includes the Titration and the Maintenance Periods, if applicable.
- Follow-up Period - from the end of the Overall Treatment Period through the end of the study.

For last assessment, the last available non-missing value will be used. Unscheduled visits that could not be mapped will not be displayed in the safety by-visit summaries, but they will be considered for the endpoint/last assessment visit.

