8.8. Electrocardiography

A 12-lead ECG will be recorded at the time points detailed in Table 3 of the study protocol. All ECGs will be performed after at least 5 minutes rest in a supine or semi-supine position. A qualified physician at a central diagnostic center will be interpreting the ECG. A central ECG Standard 12-lead ECG will record heart rate (HR), PR interval (Time from the beginning of the P wave to the beginning of the QRS complex in electrocardiogram), RR interval (Time between the start of one R wave and the start of the next R wave in the ECG), QT interval, Fridericia's corrected QT interval (QTcF), and QRS duration (Graphical deflections corresponding to ventricular depolarization in a typical electrocardiogram).

All ECG results outside of the reference ranges will be judged by the investigator as belonging to one of the following categories:

- abnormal and not clinically significant
- abnormal and clinically significant

If an abnormal post-baseline QTcF value >500 msec or change from screening >60 msec is found, the investigator must further evaluate QTcF based on protocol section 7.8.

Shifts (normal and abnormal) from baseline to overall result interpretation, each visit and last assessment, will be summarized using patient counts for the centrally-read interpretation. For overall result interpretation the worst post-baseline finding for the patient (the abnormal finding if there are both normal and abnormal findings) will be used in the summaries. Summary statistics for ECG variables values will be presented. Actual values and changes from baseline to each scheduled visit and last assessment will be summarized using descriptive statistics.

QTcF values will be classified as having QTc prolongation if any of the following conditions are met.

- Confirmed QTcF >450 msec
- Confirmed QTcF >480 msec
- Confirmed QTcF >500 msec
- Increase from screening QTcF > 60 msec
- Increase from screening confirmed QTcF > 60 msec

Screening is defined as the last non-missing ECG value prior to first dose IMP and the confirmed QTcF is defined as the average of up to 3 standard ECG values at a visit, or a single summary ECG. If there are more than 3 standard or more than one summary ECG at a visit, then use the last ECGs for the confirmed QTcF.

The number and percentage of patients with QTc prolongation will be summarized by treatment and overall, and by visit and last assessment.

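### The laboratory shift table uses the off-drug week 16 repeat for the patients with a clinically significant week 15 abnormality, so those that normalise within a week leave the count

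*SAP*

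**What the plan says.** Four statements in the SAP act together.

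- Section 8.5, on the only normal-range count: "Shifts (below, within, and above the normal range) from baseline to last assessment will be summarized using patient counts". No shift to week 15 and no worst-value shift is planned.
- Section 4.4, on what that endpoint means: "For last assessment, the last available non-missing value will be used". It is not restricted to values taken on treatment. Table 3 in the same section gives laboratory tests two post-baseline windows: day 2 to end of treatment, labelled week 15, and any later day, labelled week 16.
- Section 8.5, on who has a week 16 sample: "The assessment will be repeated at week 16 visit for patients with clinically significant laboratory abnormalities at week 15".
- Section 2.1, on drug status at that sample: "All patients will discontinue IMP at the week 15 visit and will return 1 week later".

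Section 8.5 also plans a summary on the original scale: "Laboratory values and changes from baseline to week 15 and the last assessment as defined in Section 4.4 will be presented". For continuous variables, Sections 4.1 and 8.1 make this n, mean, SD, SE, median, minimum and maximum.

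**The concern.** Whether a patient's week 15 value is replaced depends on that value. A completer with unremarkable week 15 results normally contributes an on-drug value. A completer judged to have a clinically significant abnormality contributes one taken a week after stopping. The two kinds of value then share a column.

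For the abnormal test, the repeat can leave the patient out of range or move the patient into range. It cannot add an abnormal patient to that row. The effect on the count is therefore one-directional, and it falls on the abnormalities judged most important. Prompt reversal after stopping is also a pattern compatible with a drug effect, so these are cases a safety reader would want counted. Safety is a stated objective (Section 1.3), and only one on-treatment laboratory sample is scheduled.

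**Working it through.** The SAP states no figure on this point, so there is nothing to reproduce. The check is to follow one patient through the rules and then to size the effect under stated assumptions.

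**Tracing the rule for a completer, one test**

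| Week 15 result (on drug) | Week 16 sample planned? | Value in shift table | Counted as |
|---|---|---|---|
| Within range, no significant abnormality | No | Week 15, on drug | Within range |
| Out of range, not clinically significant | No | Week 15, on drug | Out of range |
| Clinically significant, still out of range at week 16 | Yes | Week 16, off drug | Out of range |
| Clinically significant, normal at week 16 | Yes | Week 16, off drug | Within range |

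Only the last row changes category. The trace assumes that the repeat is analysed centrally, because Section 8.5 summarizes central results and only lists local ones.

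**Comparison with other safety data in the SAP**

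- ECG (Section 8.8): shifts go to each visit and to last assessment, and there is a worst-case rule: "For overall result interpretation the worst post-baseline finding for the patient".
- Vital signs (Section 8.7): abnormal-value summaries draw on all post-baseline values.
- Laboratory tests (Section 8.5): neither safeguard, although this is the domain where the follow-up sample is taken selectively.

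**Illustration**

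Input from Section 2.4: about 43 patients on TEV-50717. Everything else is assumed. Take one test and one direction, with 4 patients clinically significant at week 15, of whom k are back in range at week 16. Let m be other patients out of range in the same row but not judged clinically significant.

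Table count = m + (4 − k); on-drug count = m + 4.

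- m = 0: on drug 4/43 = 9.3%. The table shows 3/43 = 7.0% for k = 1, 2/43 = 4.7% for k = 2, 1/43 = 2.3% for k = 3 and 0% for k = 4.
- m = 3: on drug 7/43 = 16.3%. With k = 4 the table still shows 3/43 = 7.0%, all of them the milder cases.

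As a range, let p be the assumed share with a clinically significant week 15 value in the test and r the assumed share of those back in range at week 16. The expected number of such patients on drug is 43 × p. The number still in the table is 43 × p × (1 − r).

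| p | On drug | r = 50% | r = 80% | r = 100% |
|---|---|---|---|---|
| 5% | 2.2 | 1.1 | 0.4 | 0 |
| 10% | 4.3 | 2.2 | 0.9 | 0 |
| 20% | 8.6 | 4.3 | 1.7 | 0 |

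The chance that at least one case is lost is 1 − (1 − p × r)^43. At p = 5% and r = 25% this is 1 − 0.9875^43 = 42%. At p = 20% and r = 100% it is nearly 100%. A lower p gives smaller numbers throughout, and the documents give no value for p or r.

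**The case against.** The strongest reply is that on-drug data are kept and reported. Week 15 values and changes are summarized by arm, with minimum and maximum, so an extreme on-drug value in a continuous test remains visible. That stands, but it shows one extreme per arm and not how many patients were out of range. Categorical results may be counted at week 15 under Section 8.1, but no normal-range classification is planned for that visit.

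A second reply is that Section 8.3 counts patients with adverse events, and a clinically significant laboratory value may be reported as one. That is possible. Whether it must be reported is normally a protocol matter, and the protocol is not at hand. It would still depend on reporting and would not be a tabulation against the normal range.

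A third is that the rule applies equally to placebo and the table is descriptive. Both are true. Equal application does not protect the comparison if the drug causes reversible abnormalities, because the active arm would then lose more cases. But no hypothesis test, alpha allocation or interim decision depends on this table.

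A reader might infer that every abnormality reversing within a week is lost. The SAP does not support that: only clinically significant week 15 abnormalities have a planned repeat. A reader might also infer that no table anywhere in the plan would count these patients. That is safe only for Section 8.5.

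**Conclusion.** As written, the plan replaces on-drug values with off-drug values in its only normal-range laboratory count, and does so only for patients with clinically significant week 15 abnormalities. The loss is confined to those that normalise by week 16. For the affected test, the direction is toward fewer abnormal patients.

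The size is unknown and may be zero. The figures of 9.3% falling to 4.7% or lower rest on an assumed rate, on all cases being in the same test and direction, and on a central repeat. A drop to 0% also needs no milder out-of-range value in that row.

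The point should be fixed. Treating it as a serious defect would go too far: it concerns one descriptive table, the on-drug data remain in the database, and the count could be produced later, although then post hoc.

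**What to change.** In Section 8.5, tabulate the shift from baseline to the week 15 analysis visit, using the Table 3 window from day 2 to end of treatment and including early termination and unscheduled samples in that window. This can replace the shift to last assessment or stand beside it. Show week 16 repeats separately, as follow-up data for the patients retested.

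State how an early termination sample taken after the last dose is handled, and label it as off treatment. Section 2.1 places that visit after the last dose, so such a sample should not be presented as on drug.

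A worst-value shift is not needed to meet the concern. With one scheduled on-treatment sample it would largely duplicate the week 15 shift, and it needs a rule for direction in tests with both lower and upper limits.

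Cost: SAP wording and one or two table shells. No new data are needed.
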